18.1.1. All TEAEs

All TEAEs will be summarized by SOC and PT. This summary table and all other TEAE summaries by SOC and PT will be presented by descending frequency in the etrasimod group. All AEs, regardless of treatment-emergent status, will be included in an AE listing. Additionally, a listing of other AE details as collected on the CRF will be presented.

Exposure-adjusted incidence rate (EAIR) of TEAEs will be summarized by SOC and PT. Exposure is defined as the sum of either time (year) from first dose to the onset of first such event for those who experienced this AE, or time (year) from first dose to last participation for those who did not experience this AE. The EAIR is calculated as the number of subjects with the AE divided by the total exposure in subject-years.

18.1.1.1. Severity

Severity is classified as Grade 1: Mild, Grade 2: Moderate, Grade 3: Severe, Grade 4: Life-threatening, Grade 5: Death related to AE, using the Common Terminology Criteria for Adverse Events, v5.0 (CTCAE v5.0).

All TEAEs will be summarized by SOC, PT, and maximum severity, with SOC and PT presented by descending frequency. If a subject reports a TEAE more than once within a SOC/PT, the AE with the worst-case severity will be used in this summary.

18.1.1.2. Relationship to Study Treatment

Relationship is classified as “not related”, “unlikely related”, “probably related”, or “related” by the Investigator.

All related TEAEs will be summarized by SOC and PT. A “related TEAE” for the purpose of this summary is defined as a TEAE with relationship to study treatment of “probably related” or “related”.

All TEAEs will be summarized by SOC, PT, and highest relationship (as reported on the eCRF, not grouped), with SOC and PT presented by descending frequency. If a subject reports a TEAE more than once within a SOC/PT, the AE with the worst-case relationship to study treatment will be used in this summary. TEAEs with a missing relationship to study treatment will be regarded as “Related” to study treatment for summary tabulation purpose only.

18.1.2. TEAEs Leading to Discontinuation of Study Treatment

TEAEs leading to discontinuation of study treatment will be identified by action taken being recorded as “Drug withdrawal” on the Adverse Events eCRF.

All TEAEs leading to discontinuation of study treatment will be summarized by SOC and PT. A listing of all TEAEs leading to discontinuation of study treatment will also be presented.

Time to study treatment discontinuation due to liver-related AE will be summarized for the Safety Set for subjects who had such an event reported during the study. Descriptive statistics, Kaplan-Meier estimate of 25th, 50th, and 75th percentile time to event, 95% CIs, and p-value from the log rank test will be displayed. If a subject did not have the event, they will be censored at the date of last dose. If the date of last dose is missing, the date of last study visit up to Week 52 will be used. If no event is ever observed, then summary will not be generated.

Liver-related AEs are defined by either SOC of hepatobiliary disorders or PT of alanine aminotransferase abnormal, alanine aminotransferase increased, aspartate aminotransferase abnormal, aspartate aminotransferase increased, hepatic enzyme abnormal, hepatic enzyme increased, liver function test abnormal, liver function test increased, transaminases abnormal, or transaminases increased.

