5.6. Safety Set

The Safety Set will include all randomized subjects who receive at least 1 dose of study treatment. Subjects will be analyzed according to treatment received, regardless of randomization. The Safety Set will be used for all safety analyses.

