18.1.4. TEAEs Leading to Death

TEAEs leading to Death are those events which are recorded with an outcome as “Fatal” on the Adverse Events eCRF. A listing of TEAEs leading to death will be presented.

Time to death due to liver-related AE will be summarized for the Safety Set for subjects who had such an event reported during the study. Descriptive statistics, Kaplan-Meier estimate of 25th, 50th, and 75th percentile time to event, 95% CIs, and p-value from the log-rank test will be displayed. If a subject did not have the event, they will be censored at the date of last dose. If the date of last dose is missing, the date of last study visit up to Week 52 will be used. If no event is observed, then the summary will not be generated.

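### SAP 18.1.2 and 18.1.4 restrict the liver-related time-to-event summaries to subjects with the event, yet plan censoring of subjects without it and a log-rank test

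*SAP*

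**What the plan says.** SAP 18.1.2 states that time to study treatment discontinuation due to a liver-related AE "will be summarized for the Safety Set for subjects who had such an event reported during the study". It then lists the output: "Kaplan-Meier estimate of 25th, 50th, and 75th percentile time to event, 95% CIs, and p-value from the log rank test will be displayed". Two handling rules follow: "If a subject did not have the event, they will be censored at the date of last dose", and "If no event is ever observed, then summary will not be generated".

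SAP 18.1.4 repeats the design for liver-related death. Its population is again "for subjects who had such an event reported during the study", its test is again a log-rank test, and it again censors subjects without the event at last dose.

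The parent population is defined in SAP 5.6: "The Safety Set will include all randomized subjects who receive at least 1 dose of study treatment". That set includes subjects with and without liver events. SAP 18 excludes between-arm safety tests unless one is specified, so the log-rank test is a comparison the plan has chosen to make.

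**The concern.** The population phrase and the censoring rule cannot both operate as written. If the analysis holds only subjects who had the event, no one is censored, each arm's Kaplan-Meier curve falls to zero, and the log-rank test asks only whether cases on etrasimod occurred earlier or later than cases on placebo. It no longer asks whether more subjects on etrasimod had the event.

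Liver injury is a special-interest category in SAP 18.1.5. I found no other planned between-arm test specific to liver-related discontinuation or liver-related death; the risk differences in SAP 18.1.6 cover broader groups. A non-significant p-value from the event-only analysis could be taken as reassurance about frequency that it cannot give.

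**Working it through.** **Step 1. Possible readings of the population phrase.**

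| Reading | Does the censoring rule have a use? | What the log-rank test compares |
|---|---|---|
| Subjects who had the liver-related discontinuation (or death) | No, nobody is censored | Event timing among cases only |
| Subjects who had any liver-related AE | Yes | Arms after selection on a post-randomisation event |
| Whole Safety Set; the phrase only says when the table is produced | Yes | Event rates between arms as treated |

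The third reading fits the Safety Set label, the censoring rule and the no-event rule. It does not fit the phrase itself, and the phrase is not needed as a trigger because the no-event rule already covers that case. I found no other section that settles the matter.

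**Step 2. Inputs for an illustration.** The plan gives no figure to reproduce here. Arm sizes are 280 and 140 (SAP 7) and two-sided alpha is 0.05 (SAP 6.5). Dropout of 50% is taken from SAP 16.1.4.1, where it is the projected overall rate. The documents give no liver-event rates, so every count and risk below is an assumption.

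**Step 3. Worked examples.** The log-rank statistic is (O − E)²/V. O is the observed etrasimod events, E their expected number given the risk sets, and V the variance of O. Event times are spread over 52 weeks, with placebo events near the middle and no early dropout.

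| Events (etrasimod v placebo) | Set | O | E | V | Statistic | p |
|---|---|---|---|---|---|---|
| 20 v 2 | Full | 20 | 14.53 | 4.93 | 6.07 | 0.014 |
| 20 v 2 | Event-only | 20 | 20.57 | 1.25 | 0.26 | 0.61 |
| 12 v 1 | Full | 12 | 8.62 | 2.90 | 3.94 | 0.047 |
| 12 v 1 | Event-only | 12 | 12.27 | 0.65 | 0.11 | 0.74 |

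In the event-only rows E is computed from risk sets that contain only the cases. It therefore sits close to O however unequal the counts are.

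**Step 4. Rejection rates by simulation.** There were 3,000 trials per row, with exponential event times and exponential dropout reaching 50% by Week 52.

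| Assumed 52-week risk (etrasimod v placebo) | Full set | Event-only |
|---|---|---|
| 2% v 2% | 3.9% | 7.8% |
| 5% v 5% | 5.0% | 7.6% |
| 4% v 1% | 23% | 7.5% |
| 8% v 2% | 58% | 9.7% |
| 12% v 3% | 80% | 8.2% |
| 20% v 5% | 97% | 7.6% |

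The event-only test rejects about 7% to 10% of the time whatever the true difference.

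**Step 5. Percentiles on the full set.** In the 20 v 2 example, overall survival at Week 52 is 1 − 22/420 = 0.948. The 25th percentile of time to event needs the curve to fall to 0.75, so none of the three planned percentiles would be reached.

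**The case against.** The strongest reply is that the plan never intended an event-only analysis. The paragraph names the Safety Set, censors subjects without the event and suppresses the output if there are no events. All of that fits the full set, with a loosely worded phrase. This largely stands as to intent, but it does not remove the contradiction: the phrase is in both sections, and a programmer could follow it.

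Three stronger inferences are tempting and are not supported.

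- **That the planned comparison definitely conditions on the outcome.** The documents support only that the text contradicts itself and that one literal reading does so.
- **That requesting percentiles shows the restricted version will be programmed.** Percentiles can be specified before event counts are known and then reported as not estimable. The documents give no liver-event rate from which to argue otherwise.
- **That a liver signal could be lost.** SAP 18.1.6 gives counts and frequencies of liver-related TEAEs leading to discontinuation and to death, with risk differences for deaths, discontinuations and special-interest events overall. SAP 18.1.5 compares liver injury with an extended Cox model. SAP 18.3.1 adds hepatic enzyme incidences and hepatotoxicity plots. An imbalance would be visible there.

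Nor does every imbalance change the test result. With an assumed 10/280 = 3.6% against 1/140 = 0.7% (crude proportions), Fisher's exact test gives p = 0.11, so at such counts a full-set comparison would not be significant at 0.05 either.

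**Conclusion.** The concern holds as an internal contradiction in the population wording of both sections. Under the literal event-only reading the log-rank test carries essentially no information on how many subjects in each arm had the event. Under the assumed risks, its rejection rate stays at about 7% to 10% where the full-set test ranges from 23% (4% v 1%) to 97% (20% v 5%). Those figures rest on assumed risks, exponential times and 50% dropout, and show direction and scale only.

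The consequence is minor. These are safety summaries outside the multiplicity scheme in SAP 8.4, the intended analysis is probably the full Safety Set, and other planned outputs show liver-related events for all treated subjects. The correction is still worth making because the log-rank test is a specified comparison and its population should be unambiguous.

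**What to change.** In SAP 18.1.2 and 18.1.4, delete "for subjects who had such an event reported during the study". The analysis then covers the whole Safety Set with the censoring already stated. Add that any Kaplan-Meier percentile not reached is reported as not estimable.

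Showing cumulative incidence at Weeks 12 and 52 would be a useful but optional addition. If it is added, the SAP should say whether this is one minus Kaplan-Meier or a competing-risk estimate.

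The deletion costs a wording change in two sentences. It needs no new data and does not affect the efficacy analyses.

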18.1.3. Serious and Non-Serious TEAEs

Serious adverse events (SAEs) are those events recorded as “Serious” on the Adverse Events eCRF.

All serious TEAEs will be summarized by SOC and PT. If the seriousness is missing, the AE will be considered as “Serious” for summary tabulation purpose only. A serious TEAE listing will also be presented. All nonserious TEAEs will be summarized by SOC and PT.

18.1.4. TEAEs Leading to Death

TEAEs leading to Death are those events which are recorded with an outcome as “Fatal” on the Adverse Events eCRF. A listing of TEAEs leading to death will be presented.

Time to death due to liver-related AE will be summarized for the Safety Set for subjects who had such an event reported during the study. Descriptive statistics, Kaplan-Meier estimate of 25th, 50th, and 75th percentile time to event, 95% CIs, and p-value from the log-rank test will be displayed. If a subject did not have the event, they will be censored at the date of last dose. If the date of last dose is missing, the date of last study visit up to Week 52 will be used. If no event is observed, then the summary will not be generated.

18.1.5. TEAEs of Special Interest

Categories of Targeted Medical Events (TMEs) and a list of preferred terms associated with these TME categories were developed based on the mechanism of action of etrasimod, prior experience with other agents acting via a similar mechanism, and disease-specific clinical judgment. In addition, where standard testing has been implemented to screen for potential AESI (eg, electrocardiograms, spirometry, serum transaminases, etc.), the relevant data will be reviewed to identify potential cases of AESI that investigators may not have identified and to provide quantitative data for AESIs. The proposed candidate terms will be reviewed to identify which events reflect AESI.

TEAEs of special interest will be summarized by category, subcategory, and PT by descending frequency by treatment group. Categories and subcategories of TEAEs of special interest are the following:

- Cardiovascular Events
 - Bradycardia
 - AV conduction delay
 - Hypertension
- Macular Edema
- Pulmonary Disorders
 - Airflow obstruction (forced expiratory volume in 1 second [FEV₁], forced vital capacity [FVC])
 - Decrease gas exchange (diffusing capacity of the lungs for carbon monoxide [DLCO])
- Infections
 - Severe infections
 - Opportunistic infections (Narrow)
 - Herpes simplex and herpes zoster

- Liver Injury
 - Liver transaminases elevation
 - Bilirubin elevation
- Posterior Reversible Encephalopathy Syndrome (PRES)
- Malignancies

For each category, subcategory, and PT, model-based analysis will be performed to compare treatment effect between etrasimod and placebo. An extended Cox regression model will be used to handle recurring AEs (Cao 2011). The stratification variables, naïve to biologic or JAK inhibitor therapy status at study entry (Yes or No), Baseline corticosteroid use (Yes or No), and Baseline disease activity (MMS: 4 to 6 or 7 to 9), will be included in the model. A subject with K events contributes (K+1) observations to the input data set; here K might be 0. The k-th observation of the subject identifies the time interval from the start date of the (k-1)-th event, or time 0 (if k = 1), to the start date of the kth event, k = 1, ..., K. The (K+1)-th observation represents the time interval from the K-th event to the date of censorship, ie, the date of last dose or date of last study visit up to Week 52, whichever is later. Hazard ratios, 95% CIs, and p-values for treatment effect comparison will be presented.

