9.5. Follow-Up Period

For subjects not participating in the OLE study, a follow-up visit, will be performed at 2 and 4 weeks after the last administration of study treatment as indicated in the Schedules of Assessments (Table 7 and Table 8).

If the ET or Study Completion visit is ≥ 2 weeks after the last administration of study treatment, the 2-Week Follow-Up visit is not required; however, the 4-Week Follow-Up visit should be

scheduled and completed. If the ET or Study Completion visit is ≥ 4 weeks after the last administration of study treatment, the 4-Week Follow-Up visit is not required.

If the absolute peripheral lymphocyte count is not within normal limits at the 4-Week Follow-Up visit, subjects should return for CBC with differential according to local standard of care (captured as subsequent Follow-Up visit or unscheduled visit).

All adverse events should be recorded for 30 days after last administration of study treatment (Section 9.10.8.2.2).

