9.10.8.2.2. Recording Adverse Events

The adverse event reporting period for safety surveillance begins when the subject is initially included in the study (date of first signature of informed consent) and continues up to 30 days after the last administration of study treatment. If an adverse event is not resolved or stabilized by this time, the Sponsor in consultation with the Investigator will decide whether to continue to monitor the adverse event or closeout the event in the database if no further follow-up is necessary.

Any SAE suspected to be related to the study treatment must be reported whenever it occurs, irrespective of the time elapsed since the last administration of study treatment.

Investigators and study personnel will record all adverse events and SAEs whether received through an unsolicited report by a subject, elicited during subject questioning, discovered during physical examination, laboratory testing, and/or other means by recording them on the eCRF and/or SAE Form, as appropriate. The following information should be recorded on the adverse event eCRF:

- Description including onset and resolution dates
- Whether it met SAE criteria
- Severity
- Relationship to study treatment or other causality
- Outcome

For SAEs, events occurring secondary to the primary event should be described on the eCRF in the narrative description field.

The following should be considered when recording SAEs:

- Death is an outcome of an event. The event that resulted in the death should be recorded and reported on the eCRF.
- For hospitalizations, surgical, or diagnostic procedures, the illness leading to the surgical or diagnostic procedure should be recorded as the SAE, not the procedure

itself. The procedure should be captured in the narrative as part of the action taken in response to the illness.

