18.1. Adverse Events

AEs will be coded using MedDRA (v24.1). The version used to code AEs will be displayed in the analyses. Treatment-emergent adverse events (TEAEs) are defined as AEs that started or worsened in severity on or after the first dose of study treatment.

Refer to [Appendix 2](#) for handling of partial dates for AEs for the purpose of assigning treatment-emergent flags. In the case where it is not possible to define an AE as treatment-emergent or not, the AE will be classified as treatment-emergent.

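### The AESI Cox model in SAP 18.1.5 has no end date for events but stops event-free time at a censoring date, so late events can shift the hazard ratio slightly

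*SAP*

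**What the plan says.** SAP 18.1.5 compares the arms on each AESI category, subcategory and preferred term with an extended Cox model for recurring events. A subject with K events supplies K + 1 records. Record k runs from the previous event (or time 0) "to the start date of the kth event, k = 1, ..., K". The last record runs from event K to the censoring date, defined as "the date of last dose or date of last study visit up to Week 52, whichever is later".

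Which events can enter is set elsewhere. SAP 18.1 takes treatment-emergent events as "AEs that started or worsened in severity on or after the first dose of study treatment", with no closing date, and the date algorithm in SAP Appendix 2 adds none. Protocol 9.10.8.2.2 says the reporting period "continues up to 30 days after the last administration of study treatment", and adds: "Any SAE suspected to be related to the study treatment must be reported whenever it occurs".

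Off-treatment visits exist only for subjects who do not enter the open-label extension (OLE). Protocol 9.5 says that for them "a follow-up visit, will be performed at 2 and 4 weeks after the last administration of study treatment".

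Other safety summaries use other end points for time at risk. The exposure-adjusted rates in SAP 18.1.1 use "time (year) from first dose to last participation for those who did not experience this AE". The liver-related time-to-event summaries in SAP 18.1.2 and 18.1.4 censor event-free subjects at the last dose.

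**The concern.** Events and event-free time are closed by different rules. In the weeks after the censoring date, a subject who has an AESI stays in the risk set until it starts, while subjects without one have already left. Length of follow-up then depends on the outcome.

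This has two consequences. First, the data set as specified can contain records that end before they begin, and the SAP does not say what to do with them. Second, if one arm stops earlier and is then watched off drug, that arm gains more events relative to its counted time. If that arm is placebo, the etrasimod hazard ratio is pulled down, which is the less cautious direction for a safety comparison. In addition, the exposure-adjusted rate and the hazard ratio for the same AESI may rest on different time at risk.

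**Working it through.** The documents give no event rate, event count or hazard ratio for this model, so there is no planned figure to reproduce.

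**The interval problem.** Let C be the censoring date and let an AESI start d days later, with 0 < d ≤ 30. With K = 1 the records are (0, C + d], ending in an event, and (C + d, C], which has length −d. An otherwise identical subject without the event contributes only (0, C].

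**Length of the gap.** It is at most 30 days. For a subject treated for 364 days that is 30 / (364 + 30) = 7.6% of the collection time. An early termination visit 7 days after the last dose (the limit in protocol 5.1) would cut it to 30 − 7 = 23 days. If the 4-week follow-up visit counts as a visit up to Week 52, it falls to 30 − 28 = 2 days, but only for early stoppers outside the OLE whose follow-up visits precede Week 52.

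**Hand check with equal true rates.** Assumptions: 40% of etrasimod and 65% of placebo subjects stop early, uniformly between Days 14 and 364 (mean 189); the rest are treated for 364 days; all early stoppers are followed 30 days off drug; and C is the last dose.

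- Counted days, etrasimod: 0.60 × 364 + 0.40 × 189 = 294.0
- Counted days, placebo: 0.35 × 364 + 0.65 × 189 = 250.25
- Off-drug days that yield events but no event-free time: 0.40 × 30 = 12.0 and 0.65 × 30 = 19.5
- Approximate ratio: (1 + 12.0/294.0) / (1 + 19.5/250.25) = 1.0408 / 1.0779 = 0.966

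This is a rate ratio that covers early stoppers only.

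**Simulation.** A recurrent-event Cox model was fitted to 3,000,000 simulated subjects per scenario, with 2:1 allocation and constant hazards. In the as-written version, a final interval with stop before start was dropped. OLE entrants were given no 30-day follow-up in this study. Results at a placebo rate of 0.2 events per year:

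| Early stopping (etrasimod vs placebo); followed 30 days | True HR | As written | Events cut at C | Risk time extended |
|---|---|---|---|---|
| 50% vs 50%; everyone | 1 | 0.995 | 0.996 | 0.996 |
| 50% vs 50%; everyone | 2 | 1.967 | 2.008 | 2.006 |
| 50% vs 50%; early stoppers only | 2 | 1.999 | 1.998 | 2.000 |
| 40% vs 65%; everyone | 1 | 0.965 | 1.000 | 0.998 |
| 40% vs 65%; everyone | 2 | 1.898 | 1.998 | 1.997 |
| 40% vs 65%; everyone | 3 | 2.844 | 3.013 | 3.011 |
| 40% vs 65%; 30% of stoppers, 10% of completers | 1 | 0.987 | 0.998 | 0.998 |
| 40% vs 65%; 30% of stoppers, 10% of completers | 2 | 1.979 | 2.004 | 2.005 |
| No early stopping; completers | 2 | 1.942 | 1.997 | 1.997 |

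The largest shift is 2.844 / 3.013 = 0.944, or −5.6%. A placebo rate of 0.05 per year gave the same pattern (0.966, 1.890 and 2.872 for true ratios 1, 2 and 3 in the 40% vs 65%, everyone-followed case). Late events were about 10% of all events when everyone was followed, and about 2% when most entered the OLE.

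The completers-only row shows a second source of shift. After Week 52 the risk set holds almost only subjects who go on to have an event, and this pulls a ratio above 1 back towards 1. Either way of aligning the windows recovers the true ratio within simulation error.

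**The case against.** The strongest defence is that running the last record from event K to censoring makes sense only if event K comes first, so K may be meant to count events up to censoring. That would remove the problem, and it may be the intention. But the SAP does not say it, and neither SAP 18.1 nor Appendix 2 puts an upper limit on event dates.

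Next, taking the later of two dates already helps. If follow-up visits count, most of the gap closes for early stoppers outside the OLE. Blinded drug dispensed at Week 52 to bridge to the OLE (protocol Table 8, footnote r) can also move the last dose past Week 52. Both points stand as limits on size. Against the first, SAP 6.4 keeps follow-up visits out of the visit windows and Appendix 1 lists them as a separate period, so counting them is not the obvious reading. On either reading, the follow-up visits of Week 52 completers fall after Week 52, and the 30 days after Week 52 stay uncovered for completers outside the OLE unless their last dose is later.

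Two stronger readings are tempting and are not supported. A reader might infer that late events have no time at risk at all. They do: the subject's own record runs to the event, and what is missing is the time of event-free subjects. A reader might also infer that the hazard ratio is biased outright. It is not when the true ratio is 1 and the arms stop and are followed alike.

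Finally, little depends on the shift. For illustration, with 20 and 10 events the standard error of the log hazard ratio is √(1/20 + 1/10) = 0.39, so a 4% shift is about 0.1 standard errors. That is fair, and it is why the point is minor.

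**Conclusion.** The point holds as a minor defect in a safety analysis. Followed literally, SAP 18.1.5 makes follow-up depend on having a late event and can produce a final interval with stop before start. The hazard ratio can then be off by a small amount: 0 to about 6% in the scenarios tried, and about 1% when most subjects enter the OLE.

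These sizes rest on assumed event rates, stopping rates by arm and OLE shares. The documents give only a projected overall dropout of 50% (SAP 16.1.4.1), with no split by arm and no OLE figure. The direction is therefore not established. More stopping on placebo lowers the ratio; more stopping on etrasimod would be expected to raise it, though that case was not simulated. The AESI risk differences in SAP 18.1.6 do not use this time at risk, and neither do the primary and key secondary efficacy analyses.

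**What to change.** In SAP 18.1.5, give events and time at risk the same end date. The simplest way is to count in the Cox model only events that start on or before the censoring date already stated. The cost is that a few late, off-drug events leave this model; they remain in the incidence tables.

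The alternative is to extend every subject's time at risk to the end of adverse event collection: 30 days after the last dose, or OLE entry if earlier. That keeps the late events but adds off-drug time to the comparison.

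In either case, state whether the 2- and 4-week follow-up visits count towards the last visit up to Week 52, require stop after start for every interval, and align with, or explain the difference from, the time at risk in SAP 18.1.1. This takes a sentence or two in the SAP and a small change to the derivation, settled before unblinding.
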